#### **INFORMED CONSENT:**

All participants will provide written, informed consent, before engaging in any study procedures. Participants will be given as much time as they need to provide consent, including taking the consent form home to read and enrolling at a later date (provided they still enroll while they are a patient in the partial hospital). The consent form will be explained fully by a member of the study staff before signing.

#### **CONFIDENTIALITY OF DATA:**

Data will be kept in locked cabinets in locked rooms and on secure, limited access servers behind The Miriam Hospital firewall. On survey documents and in the survey databases, participants are identified only by only numeric IDs, so the identity of participants is protected. The document connecting participant names to IDs will be kept separate from study data.

#### **DATA AND SAFETY MONITORING PLAN:**

Given that the proposed research is a single site, pilot RCT, with a very short duration of active participant contact and our expectation of a minimal risk designation, the proposed trial does not meet NIH criteria requiring establishment of a formal Data and Safety Monitoring Board. However, we have a detailed data and safety monitoring plan to ensure the safety of all participants and the validity and integrity of the data.

#### Monitoring.

[name] (PI) will have primary responsibility for monitoring all participants. Any data or safety issues that arise will also be discussed with [name], a senior investigator with extensive experience conducting tobacco cessation research with patients with mental illness, who will provide consultation. In addition, an independent faculty member will be recruited before the start of the study to serve as an independent reviewer. Drs. [name], [name], [name], and the independent reviewer will meet quarterly to review study progress and the occurrence of adverse events.

In addition, The Miriam Hospital IRB will initially approve the study. All needed changes or amendments to the IRB approved protocol will be submitted to the IRB in a timely manner. There will be no changes in protocol enacted until IRB approval of the new protocol is received.

[name] will report all adverse events to The Miriam Hospital IRB within 24 hours. The funding institution will be informed in cases when any significant action is taken as a result of an adverse event or by direction of the IRB. Any serious adverse event (SAE), whether or not related to study intervention, will be reported to both the IRB and the funding institution. A summary of the SAEs that occurred during the previous year will be included in the annual progress reports to both the IRB and the funding institution.

#### Data.

All data and records will be safeguarded according to the policies of The Miriam Hospital IRB. As reviewed above, all participant records and assessment data from this study will be treated as confidential, including participant names and the fact they are participating in the study. All electronic data will be stored on secure, password protected servers. A file will be maintained that associates the subject's name with that subject's study identification number. This file will be kept in a secure, password-protected file, separate from the actual study data (e.g., screener and survey data). This study will use electronic data collection for all study data. However, consent forms will be paper forms. They will be stored in locked file cabinets in a locked room.

Long-term storage of these paper files will be at a facility that specializes in the storage of medical/research information. The destruction date of these files will be at least 6 years from the termination of the study and will be authorized by the PI.

Only the Principal Investigator, co-Investigator, and study staff will have access to data. The data entry system will require login identification and passwords in order to gain access to the data. All data are considered part of the subject's confidential record. All staff will receive ethics training and will be trained by [name] (PI) in strict confidentiality procedures.

Every effort will be made to ensure that missing data are kept to a minimum. Data entry programs with range checking and response validation will be used for any data keypunched. Where appropriate, validation and range rules will be applied to the actual entry fields. Under supervision from the PI, the Data Systems Analyst will conduct error checking procedures and preliminary analyses on all data to ensure their accuracy. All data designated as primary outcome data will be subject to a 100% cross-referencing. All data files are automatically backed-up daily. All audits will be supervised and documented by the PI.

Only the Principal Investigator will give permission for the release of aggregated study data. No identifiable data will be released. Participants in the proposed research will be informed, during consent, that completely de-identified data (i.e., data that has been cleaned of all 18 types of HIPAA identifiers) will be available to other qualified researchers. Within 18 months of study completion, we will make datasets available to interested investigators who submit a written request to the PI. The only contingency on the use of the data will be that ethical guidelines be followed (e.g., only individuals who have completed a research ethics training course will have access to the data, the data will be stored securely). The NIH will be notified of transmissions of the data to interested investigators.

#### Education/Training.

All research personnel connected with this project will participate in mandatory education in human research subject protection. At the core of the self-directed training program is the tutorial provided through the Collaborative Institute Training Initiative (CITI) hosted by the University of Miami. All staff must complete online training in the protection of human research subjects and units specific to HIPAA regulations and compliance. To be certified, all staff must pass the CITI training every 3 years and the HIPAA unit annually. All investigators and staff on the present application have been certified and will maintain certification.

Study Title: Acceptance and Commitment Therapy for Tobacco Cessation Among Psychiatric Partial hospital Patients

NCT#: NCT03911960

Date: July 1st, 2020

Data analysis.

Due to small sample sizes, analyses will be descriptive.

Aim 1. To assess the feasibility of the proposed ACT-based counseling program, we will conduct descriptive statistics on number of patients recruited to the program during the enrollment period compared to number of smokers seen in the PHP during the enrollment period. In addition, we will conduct descriptive statistics on the number of sessions completed per group and rates of completion of the follow-up visit. To assess acceptability of the program, we will report descriptive statistics of responses on the Client Satisfaction Questionnaire in each group. To evaluate the safety of offering a tobacco cessation intervention during a PHP, we will report on the number of participants in the trial who are rehospitalized for a psychiatric reason during the treatment period based on participant self-report at end of treatment. To assess for symptom exacerbation we will report means of psychiatric symptoms by group pre and post intervention among those who completed follow-up.

Aim 2. To evaluate for preliminary evidence of efficacy, we will report abstinence rates by group at end of treatment. Those lost to follow-up will be considered smokers.

Aim 3. To assess for the effect of treatment condition on ACT treatment targets, we will report descriptive statistics of treatment targets before treatment and at follow-up for those who completed the follow-up visit.

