#### Measures.

Feasibility, acceptability and safety. Feasibility of recruitment and retention will be measured by the proportion of smokers seen in the program during the enrollment period who enroll during the recruitment period. The two existing studies of smoking cessation treatment provided in inpatient psychiatric hospitals reported 69-79% recruitment rate (of those meeting inclusion criteria) and 80% retention. Results in this range will be considered feasible. Feasibility of treatment delivery will be assessed by the number of completed visits in the ACT group. Previous studies of ACT for tobacco cessation have found approximately 65-67% of calls were completed. Results in this range will be considered feasible. Acceptability will be measured at end of treatment using the 8-item Client Satisfaction Questionnaire (CSQ), a reliable and valid questionnaire developed to test health program acceptability. Safety. We will collect information on patient re-hospitalization via chart review and using questions from the 2016 National Health Interview Survey about visits to the emergency room and to the hospital. In addition, we will assess for symptom exacerbation. In addition, we will measure global distress using the K6 scale, a measure of non-specific psychiatric distress that has been used in population samples to discriminate between samples with and without mental illness.

Efficacy. Efficacy will be measured by 7-day point-prevalence tobacco abstinence at end of treatment, verified by an expired breath CO rating  $\leq 6\text{ppm}$ . Finally, we will assess number of serious quit attempts ( $>24$  hours of intentional abstinence).

ACT treatment targets. ACT treatment targets will be measured at both in person visits and during the follow-up call. The two overarching constructs of ACT, acceptance, and commitment will be assessed. Acceptance, will be measured using the Avoidance Inflexibility Scale (AIS), a 13 item, Likert scale, assessing participants' responses to their internal stimuli, including smoking-related thoughts, feelings and physiological sensations. Acceptance has been shown to account for the bulk of the treatment effect of ACT for tobacco cessation in previous studies. Commitment will be measured using the 8-item, Commitment to quitting scale (CTQ).

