Worsening of psychiatric symptoms and emergent suicidality. Available evidence suggests that quitting smoking has not been associated with increases in psychiatric symptoms among those with mental illness and may even result in improvement in psychiatric symptoms. However, this population is at high risk for additional acute psychiatric episodes.

Need for adjustment of psychiatric medication following cessation: Cessation in some patients on psychiatric medications (most notably antipsychotics, benzodiazepines, SSRIs, SNRIs and tricyclic antidepressants) can produce increased serum drug levels. Medication doses will need to be monitored upon cessation to maintain the proper therapeutic dose.

Confidentiality or loss of privacy. We will collect potentially sensitive information about participants; if released inappropriately, participants may experience embarrassment or distress. The seriousness of the consequences would depend on the nature of the information revealed and to whom the information was revealed. Given the numerous steps we take to protect participant confidentiality, we think the risk of a breach of confidentiality is low.

Discomfort or distress when completing assessment and treatment procedures. Some participants may feel uncomfortable or distressed answering personal or private questions during assessment or treatment. In our previous studies, when individuals do report discomfort in these situations, it is mild. Participants will be informed at the beginning of each assessment that their participation is voluntary and they may refuse to answer any questions that make them uncomfortable or withdraw from the study at any time.

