As part of the Partial Hospital program, all patients are referred to a psychiatrist and a therapist upon discharge. We will obtain a release to inform these mental health providers that their patient is attempting to quit smoking and could experience symptom exacerbation. Participants will be informed that, in the case of symptom exacerbation, they should: (1) discuss the symptoms with their psychiatrist, therapist and/or primary care provider, (2) page [name], a licensed psychologist ([name], a licensed psychologist, will cover if [name] is not available); or, if they pose an immediate risk to themselves or someone else, (3) call 911 or present to the nearest emergency room.

If a participant reports active suicidality (i.e., any recent suicidal attempts, suicidal gestures, or self-injurious behavior; any current plan or intent to engage in suicidal or self-injurious behavior) to any study staff at any time, the participant will be assessed by [name] or [name], who will respond in an appropriate and ethical manner according to the standards of care for suicide prevention (e.g., referral to immediate emergency psychiatric care if danger to self is imminent).

Minimization of risk of inappropriate psychiatric medication dose upon cessation: Upon enrollment in the study, we will inform the patient's PHP psychiatrist of the patient's planned cessation attempt. A benefit of stopping smoking while in the PHP is that patients meet with their psychiatrists daily while in the program to monitor medication effects and side effects. In addition, we will obtain a release of information from the patients to their outpatient psychiatric provider and primary care provider. Upon enrollment, we will fax these providers a form letter indicating that the patient plans to attempt to stop smoking, their anticipated quit date, that they will be using the nicotine patch, and information on potential medication interactions with tobacco cessation.

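### The SAP's only safety event count is psychiatric rehospitalisation, so emergency visits, non-psychiatric admissions and SAEs that the protocol collects or reports have no place in the safety result

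*SAP*

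**What the plan says.** The SAP's safety text, in Aim 1, has two parts. The first is an event count: "the number of participants in the trial who are rehospitalized for a psychiatric reason during the treatment period", obtained "based on participant self-report at end of treatment". The second is a symptom summary: "To assess for symptom exacerbation we will report means of psychiatric symptoms by group pre and post intervention among those who completed follow-up". The symptom means are promised by group. For the event count, no split by arm and no denominator are stated.

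The protocol's Safety paragraph under Measures is wider. "We will collect information on patient re-hospitalization via chart review and using questions from the 2016 National Health Interview Survey", and those survey items cover emergency-room as well as hospital visits. No restriction to psychiatric reasons is stated. The same paragraph adds symptom exacerbation and the K6 distress scale.

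Under Monitoring, all adverse events go to the IRB within 24 hours. For the serious ones: "Any serious adverse event (SAE), whether or not related to study intervention, will be reported to both the IRB and the funding institution". Quarterly review meetings include an independent reviewer.

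Under RISKS, the protocol names patch side effects, worsening psychiatric symptoms with emergent suicidality, and the effect of quitting on psychiatric medication, which "can produce increased serum drug levels".

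**The concern.** The SAP sets out to evaluate how safe it is to offer cessation treatment during the partial hospital programme. Its event definition is narrower than both the data the protocol gathers and the harms the protocol names. A patch reaction or a drug-level effect could lead to an emergency visit or a medical admission. A suicidal crisis could be dealt with in an emergency room without admission; the protocol itself directs participants at immediate risk to emergency services. None of these would enter the count.

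At stake is whether the reported safety result describes what happened. Followed as written, the SAP could show no psychiatric rehospitalisations and say nothing of other acute-care events already in the trial's records. Because a split by arm is not promised, a difference between ACT Care and Enhanced Usual Care in the one event that is counted might also go unshown.

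**Working it through.** The plan states no safety figure to reproduce, so the main check sets the two documents side by side.

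| Item | Protocol | SAP safety text |
|---|---|---|
| Psychiatric rehospitalisation | Chart review and survey | Counted, self-report only, arm split not stated |
| Non-psychiatric admission | Same sources, no limit by reason stated | Absent |
| Emergency-room visit | Survey items | Absent |
| SAE | Reported to IRB and funder, annual summary | Absent |
| Other adverse events | Reported to IRB, quarterly review | Absent |
| Psychiatric symptoms | K6 at enrolment and end of treatment | Means by group, completers only |
| Active suicidality | Response procedure, no data field described | Absent |

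Of the event types that the Safety paragraph collects or that must be reported as SAEs, one is analysed. Three are not: non-psychiatric admissions, emergency visits and SAEs.

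**Denominators.** A fuller table needs the right base for each row. Inputs: 20 per group (protocol, Sample size) and the 80% retention benchmark (protocol, Measures).

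- Total: 20 × 2 = 40.
- Expected end-of-treatment reports: 0.80 × 40 = 32. Without a report: 40 − 32 = 8.
- For x self-reported events, (x/40) ÷ (x/32) = 32/40 = 0.80. Dividing by everyone randomised would give four fifths of the percentage among those who actually reported.

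**What a zero count could rule out.** This is context only, since the SAP plans no confidence limits. With no events in n people, the one-sided 95% upper limit is 1 − 0.05^(1/n).

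| n | Meaning | Upper limit |
|---|---|---|
| 40 | All randomised | 7.2% |
| 32 | 80% of 40 | 8.9% |
| 20 | One arm | 13.9% |
| 16 | 80% of one arm (assumes equal retention) | 17.1% |

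Even a clean result on the one counted event would be weak evidence of safety, which is a further reason to report the other events in hand.

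**Unequal contact.** ACT Care has 1 in-person and 6 telephone contacts, 7 in all. Enhanced Usual Care has 1 in-person and 1 telephone session, 2 in all, before referral to the state quitline. Events that surface only when a participant mentions them to study staff have more chances to surface under ACT Care.

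**The case against.** Several points against the concern are sound and limit it.

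- A reader might infer that psychiatric rehospitalisation is the whole safety analysis. It is not: symptom means by group are also planned. They do not replace event counts, because a group mean among completers can hide one or two serious deteriorations.
- A reader might infer that suicidality responses are data going unused. The section on protection against risk begins that procedure with "If a participant reports active suicidality" and describes a clinical response, with no instrument, schedule or data field. Such events can be tabulated only where they are recorded as adverse events or SAEs. Given the unequal contact, a separate by-arm row could also show a spurious ACT excess.
- A reader might infer that SAEs go unreported. They do reach the IRB, the funder and the quarterly review. Oversight is not the trial's analysis, however, and the SAP's safety result still omits them.
- A reader might infer that the result is biased towards safe. The SAP sets no safety threshold or decision rule, and the documents do not say how often the named risks would present as something other than a psychiatric admission. The omission is shown; a bias of known size is not.
- A pooled count does partly answer the stated question, since both arms receive cessation counselling and a patch offer. With 20 per arm, only a gross imbalance could be seen. A split by arm is still reasonable, and the SAP already gives one for sessions, satisfaction, symptoms and abstinence.
- The population is described as at high risk of further acute psychiatric episodes, so psychiatric rehospitalisation is a defensible lead outcome.

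What remains is that emergency visits, non-psychiatric admissions and SAEs have no planned place in the safety result.

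**Conclusion.** The point holds as a gap in reporting. The SAP's only safety event count omits three kinds of event that the protocol collects or requires to be reported, and some of these are a plausible form for the risks the protocol lists. This rests on the text of both documents and needs no assumed event counts. Its numerical effect cannot be estimated, because no event rates are given. The figure of about 8 participants without an end-of-treatment report assumes that the 80% benchmark is met exactly. The change is worth making because safety is a stated part of Aim 1 and the remedy is cheap. It does not call the trial's safety oversight into question.

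**What to change.** In SAP Aim 1, keep psychiatric rehospitalisation as the lead item and add one descriptive table, by arm and overall, of the number and percentage of participants with:

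- any emergency-room visit;
- any hospitalisation, split into psychiatric and non-psychiatric;
- any SAE, including suicidality events where recorded as adverse events or SAEs (those recorded only as adverse events shown on their own line).

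For self-reported items, use participants with an end-of-treatment report as the denominator. For chart-review and SAE items, use all randomised participants. Show the number missing for each row. Restore chart review as a source for hospitalisation, as the protocol's Measures section provides, so that people who miss the follow-up visit are not lost from that row. Add a note that contact with study staff differs by arm, so spontaneously reported events may be detected unequally.

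The cost is SAP wording and one extra table from information the protocol already gathers, with no new visits or instruments. The downside is a safety summary that may look slightly less favourable.

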Several pilot studies show promise for ACT as a treatment for tobacco dependence, including one showing favorable results compared to traditional cognitive behavioral approaches. To date, no large scale (fully powered) trials have been completed on the use of ACT for tobacco cessation.

Most of the ACT for smoking cessation studies have included only non-psychiatric populations. ACT may be particularly well-suited for tobacco cessation in patients with psychiatric comorbidities as: (1) ACT treatments can also be applied to treat mental health symptoms allowing for a consistent treatment framework across diagnosis, (2) the hypothesized mechanism of change (i.e., willingness to experience distress and discomfort in order to live a valued life) may be particularly relevant for smokers with psychiatric comorbidities, who are more dependent and have more severe withdrawal symptoms (i.e., they will experience more

discomfort than average when quitting). There have been two, small, uncontrolled, feasibility studies of ACT for smoking cessation in patients with mental illness. These studies found ACT for tobacco cessation to be feasible in smokers with bipolar disorder and posttraumatic stress disorder. There have been no controlled trials of ACT for smoking cessation in patients with psychiatric comorbidities. More work is needed to assess the feasibility of applying the ACT treatment approach to tobacco cessation treatment with smokers with SMI, particularly among those in acute psychiatric episodes.

**SUBJECT RECRUITMENT:** Source. Participants will be recruited from the Rhode Island Hospital (RIH), Psychiatric Partial Hospitalization program (PHP; See letter from [name], Medical Director of the program). This day treatment program (8AM-2PM) employs the principles of ACT via four group sessions, and individual meetings with both a psychologist and a psychiatrist.

Sample size. We propose a sample size of 20 smokers per group because the primary aim of the R03 grant mechanism is to assess initial feasibility. We will oversample men such that 50% of the sample is male. Based on the current census of the PHP, we anticipate 240 smokers will be seen over the 8-month recruitment period, making it feasible to recruit 40 smokers.

Inclusion criteria. Participants will be male and female, current daily smokers,  $\geq$  age 18, have regular telephone access, and are able to read and write English.

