## PROCEDURES:

Recruitment. Participants will be recruited during PHP treatment. As standard clinical care, all patients are screened for smoking status upon admission. Current daily smokers will be informed about the study at that time and invited to be screened for participation. All women of childbearing potential who would like the nicotine patch will complete a pregnancy test prior to inclusion into the study. Eligible and interested participants will complete an enrollment/pre-quit visit while enrolled in the PHP, which includes a baseline assessment, random assignment to a condition, the first counseling session and 4 weeks of nicotine patches (to be started on the quit day). The enrollment visit can be on the same day as the first pre-quit visit counseling but doesn't need to be. Participants will then complete a second pre-quit counseling session (within one week of the pre-quit session but before discharge). If the participant is to be discharged before their first or second counseling session, the counselor will choose one of the following options in order of preference ((1) complete the second counseling session early but not on the same day as the first counseling session,(2) have the patient return to the partial hospital program location for the first or second counseling session, (3) complete the counseling session by phone and mail materials distributed during the counseling session). Following the second counseling session, participants will continue in their assigned post-discharge intervention consisting of up to 5 Quitline or ACT telephone sessions.

Study outcomes will be assessed at the end of the counseling treatment at an in-person visit 5 weeks after their visit 2 date OR 24 hours after the last counseling session by a research staff member, whichever is later. As an incentive for completion of the follow-up assessment, those in either group who complete this visit will receive \$20 compensation and an additional 4 weeks of the nicotine patch. We will try to schedule visits around existing appointments in the hospital system to increase compliance.

Randomization will use block randomization, unknown to the counselor or the participant. In order to balance any benefit of bupropion treatment in combination with the nicotine patch across treatment conditions, randomization will be stratified by bupropion use.

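### SAP Aim 1 counts psychiatric rehospitalisation from end-of-treatment self-report alone and leaves out the protocol's chart review, the one planned source that does not need the participant to attend

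*SAP*

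**What the plan says.** SAP Aim 1 gives two safety summaries. The first is the number of trial participants "who are rehospitalized for a psychiatric reason during the treatment period based on participant self-report at end of treatment". It names no other source, gives no denominator and does not ask for a split by arm. The second concerns symptoms: "we will report means of psychiatric symptoms by group pre and post intervention among those who completed follow-up". The same aim also reports "rates of completion of the follow-up visit". For abstinence (Aim 2) the SAP counts people without follow-up as smoking, and for the ACT targets (Aim 3) it restricts the summary to completers. It has no corresponding rule for rehospitalisation.

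The protocol's Measures section (Safety) plans two sources: "We will collect information on patient re-hospitalization via chart review and using questions from the 2016 National Health Interview Survey". Table 2 schedules rehospitalisation at end of treatment only. The Procedures section fixes when and how outcomes are obtained: "Study outcomes will be assessed at the end of the counseling treatment at an in-person visit 5 weeks after their visit 2 date". Where counselling finishes too late for that date, the visit instead follows the final session by 24 hours. A telephone follow-up appears once, in the paragraph on treatment targets: "ACT treatment targets will be measured at both in person visits and during the follow-up call". On sample size the protocol says "We propose a sample size of 20 smokers per group".

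**The concern.** The SAP is dated July 2020 and the protocol September 2019. Between the two, the safety count loses one of its two sources, and neither document comments on the change. The source that remains needs the participant to return and to report the admission. The other SAP safety summary, the symptom means, is also limited to completers, so both safety results depend on follow-up.

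Chart review could find admissions in people who never come back, and admissions that attenders leave out. Under the SAP wording neither kind enters the count. The count is nevertheless described as covering trial participants, so a person with no self-report can pass silently as not rehospitalised. What is at stake is how the safety result of the pilot is read: a low or zero figure could look more reassuring than the data support.

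**Working it through.** The plan states no event rate, power or margin for this outcome, so there is no figure of its own to reproduce beyond the total sample: 2 × 20 = 40.

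**Inputs**
- Randomised: 40, or 20 per arm (protocol, Subject Recruitment, sample size).
- Retention benchmark: 80%, from earlier inpatient studies that "reported 69-79% recruitment rate (of those meeting inclusion criteria) and 80% retention" (protocol, Measures). It is not a projection for this trial.
- Lower comparison: 67% retention in earlier telephone-delivered ACT (protocol, ACT Care).
- Event counts and event rates: assumptions, because the documents give none.

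**Direction.** Let x be the number of participants who self-report an admission. Let a be the number without a self-report in whom charts show one, and b the number who gave a self-report, mentioned no admission, and have one in the chart. The SAP count is x. The either-source count is x + a + b. Since a and b cannot be negative, leaving chart review out can lower the count or leave it unchanged, and cannot raise it.

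**How many could be affected through a**
- At 80% retention: 40 × 0.20 = 8 without a self-report, or 20 × 0.20 = 4 per arm if loss is equal.
- At 67%: 40 × 0.67 = 26.8, about 27 with a self-report and 13 without.
- Each participant of unknown status widens the possible range by 1/40 = 2.5 percentage points overall, or 1/20 = 5 points within an arm.

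**Worst-case range, x/40 to (x + unknown)/40**
- x = 0, 80% retention: 0/40 to 8/40, or 0 to 20%.
- x = 2 (assumed), 80% retention: 2/40 to 10/40, or 5 to 25%.
- x = 0, 67% retention: 0/40 to 13/40, or 0 to 32.5%.

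These are ordinary missing-data bounds and would apply to any yes/no outcome with that much loss. They do not measure what leaving out chart review costs. That cost is a + b, and the documents give no basis for estimating it.

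**Denominator alone.** With x = 2 and 32 self-reports, the figure reads 2/40 = 5.0% or 2/32 = 6.3%.

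**When attendance matters (assumed rates, 32 with and 8 without a self-report, all admissions reported by attenders)**
- 10% in both groups: the true rate is (3.2 + 0.8)/40 = 10%. Self-reports over 40 give 3.2/40 = 8%; over 32 they give 10%. The completer proportion is unbiased.
- 10% in completers and 30% in the others: the true rate is (3.2 + 2.4)/40 = 14%. Self-reports give 8% over 40 and 10% over 32. Neither denominator recovers the missing events.

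**The case against.** The strongest case on the other side has five parts.

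- **No direct contradiction.** The protocol says what will be collected, and the SAP says what will be reported. The SAP is later and names its source openly, so the narrowing may be deliberate. This stands. A reader might infer that the documents conflict or that chart review was abandoned, but they show only an unexplained choice of source.
- **The denominator is largely recoverable.** A count based on self-report comes naturally from those who gave one, and the SAP reports follow-up completion. This stands too: the missing denominator alone would be a matter of clarification. Completion rates cannot, however, supply events that only the charts would show.
- **The worst-case ranges are generic.** This stands. A reader might take 20% as the likely understatement, but that figure needs every non-reporter to have been admitted. Nor does every missing report flatter the trial, since a non-reporter without an admission hides nothing.
- **Nothing links attendance to readmission.** This is correct. A readmitted participant may plausibly be less likely to attend, but the documents do not show it. It is also not certain that every non-attender goes unasked, although the follow-up call is mentioned only for the treatment targets.
- **The count is descriptive in a 40-person pilot.** This stands and limits the severity. Serious adverse events go to the IRB and the funder under the protocol's Monitoring section, so the documents do not support an inference that participants are left unprotected. The SAP does not link that reporting to this count.

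**Conclusion.** The concern holds as a correctable weakness in a descriptive safety summary. The SAP relies on one of two planned sources, and the one left out is the one that needs no attendance. The resulting count can be too low, and the omission cannot make it too high. The size of any shortfall is unknown. About 8 of 40 without a self-report is an illustration at a borrowed 80% benchmark, and the actual number depends on this trial's retention.

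The conclusion assumes that the SAP is followed as written and that chart review can be done for participants who do not return. It does not rest on any link between readmission and attendance, since it also covers admissions that attenders fail to mention. It does not extend to a claim that the trial's safety finding is wrong or that safety oversight is deficient. No test, threshold or stopping decision uses the count. Severity is minor to moderate.

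**What to change.** Replace the rehospitalisation sentence in SAP Aim 1 with wording along these lines:

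> A participant is counted as rehospitalised if chart review or self-report shows a psychiatric admission between enrolment and the follow-up visit or, where there is no visit, within a fixed window from randomisation that is the same in both arms. We will report the number with an event over all randomised, the number with an event over those with a self-report, and the number with no self-report, overall and by arm. Participants with chart review only and no admission found will not be described as confirmed event-free.

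The window for non-attenders should run from randomisation. The planned visit date depends on visit 2 and on the last counselling session. Someone without a visit 2 has no such date, and in the enhanced usual care arm the later calls are made by the state quitline, so the study may not know when the last one took place. The investigators should set the length of the window before they look at the data. The split by arm goes beyond the SAP's present wording, but it shows whether missing self-reports are balanced.

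If chart review was dropped, the SAP should say so and report the count over participants who gave a self-report, with the number of unknown status.

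If the planned chart review was done, the cost is SAP wording and a little more tabulation. If it was dropped, the cost is a sentence and a stated denominator, with no new data. The limitation is that charts may miss admissions outside the hospital system, which is why self-report stays as a source.
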